## 6.11 Safety Analyses

The safety analyses will be presented by the treatment received for the Safety Analysis Set.

### 6.11.1 Adverse Events

All AEs will be coded by system organ class (SOC) and preferred term (PT) using the latest version of the Medical Dictionary for Regulatory Activities (MedDRA, version 24.0 or higher) and summarized by treatment and total.

The following tables/Listings will be presented for TEAEs:

- Overall incidence and the number of TEAEs, Treatment Related TEAEs, Serious TEAEs and Serious Related TEAEs. TEAEs will also be presented by Severity and Relationship
- TEAE by system organ class and preferred term, incidence and number of events.
- Treatment related TEAE by system organ class and preferred term, incidence and number of events.
- Serious TEAE by system organ class and preferred term, incidence and number of events.
- TEAEs leading to early withdrawal by system organ class and preferred term, incidence and number of events.
- TEAE by system organ class, preferred term and maximum severity, incidence. If a subject had multiple occurrences of the same PT within a treatment period, it is counted once with maximum severity under the PT; if a subject had multiple PTs within the SOC with different grades of maximum severity, it is counted once within each applicable severity grade within the SOC and Any TEAE categories.

QMD Ref: Worldwide-TMP-ST-006-4.0 Effective: 12Aug2019	Governing QMD: Worldwide-SOP-ST-001
Confidentiality Statement	

This document is the property of Worldwide Clinical Trials Inc. and may not be duplicated, copied, altered or removed from company without prior approval from Worldwide Quality Assurance or in compliance with Worldwide Standard Operating Procedures.

Worldwide Clinical Trials Controlled Quality Management Document			
 WORLDWIDE CLINICAL TRIALS	Sponsor:	Cassava Sciences, Inc	
	Protocol Number:	PTI-125-05	
STATISTICAL ANALYSIS PLAN – PHASE 1			

- TEAE by system organ class, preferred term and closest relationship, incidence. If a subject had multiple occurrences of the same PT within a treatment period, it is counted once with closest relationship under the PT; if a subject had multiple PTs within the SOC with different grades of closest relationship, it is counted once within each applicable relationship category within the SOC and Any TEAE categories.
- Listing of Serious TEAEs (presented in the Table section of the appendices).
- Listing of Deaths (presented in the Table section of the appendices).

All AEs will be separately listed.

In Mock Shells: Tables 14.3.1.1 to 14.3.1.7, Tables 14.3.2.1 to 14.3.2.2, Listing 16.2.7.1

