### 6.3 Conventions

All clinical data listings, summaries, figures and statistical analyses will be generated using SAS (Version 9.4 or higher).

QMD Ref: Worldwide-TMP-ST-006-4.0 Effective: 12Aug2019	Governing QMD: Worldwide-SOP-ST-001
Confidentiality Statement	

This document is the property of Worldwide Clinical Trials Inc. and may not be duplicated, copied, altered or removed from company without prior approval from Worldwide Quality Assurance or in compliance with Worldwide Standard Operating Procedures.

Worldwide Clinical Trials Controlled Quality Management Document			
 WORLDWIDE CLINICAL TRIALS	Sponsor:	Cassava Sciences, Inc	
	Protocol Number:	PTI-125-05	
STATISTICAL ANALYSIS PLAN – PHASE 1			

Summaries of the clinical data will be presented by treatment group / sequence or overall.

PK data listings, tables, figures, and statistical analyses will be generated using Phoenix® WinNonlin® (Version 8.1 or higher, Certara, L.P.) or SAS® (Version 9.4 or higher, SAS Institute Inc.). PK concentration-time data will be summarized by the number of non-missing observations (n), arithmetic mean (mean), standard deviation (SD), median, minimum (min), maximum (max), and coefficient of variation (CV%). PK parameter data will be summarized by n, mean, SD, median, min, max, CV%, geometric mean, and geometric CV%. Summary statistics that are not calculable due to lack of quantifiable data will be presented as NC in the descriptive statistic tables.

Treatment labels will be displayed as follows:

Fasted Simufilam	Low fat fed Simufilam	High fat fed Simufilam	Phase 2 Simufilam

Sequence group labels will be displayed as follows:

Sequence A	Sequence B	Sequence C	Sequence D

*Note: Footnotes will be added in all TLFs to clarify each sequence.*

Listings will be sorted in the following order subject, period, visit / date and parameter unless otherwise stated. All data will be listed, subjects who were not randomized will be displayed after the randomized treatment / sequence groups.

Safety parameters (continuous variables) will be summarized by the number of non-missing observations, mean, median, standard deviation, and minimum and maximum.

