Categorical variables will be summarized by presenting the frequency and percent. Percentages will be based on the number of non-missing observations or the subject population unless otherwise specified. For each variable, all categories will be shown. Zero frequencies (but not the percent) within a category will be presented.

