## 9 LIST OF TABLES, FIGURES AND LISTINGS

The following table includes details of the tables, figures and listings to be included within each section of the electronic common technical document (eCTD). The eCTD section is shown in bold. The following validation methods maybe used:

- Independent programming of numbers and manual review of format (IP)
- Independent programming by statistician of numbers and manual review of format (Stat IP)
- Manual review (MR)
- Code review (CR)

Table Number	Table Title	Validation Method	Shell Number (if repeat)
Items in bold are not table titles but references to the section headings within eCTD.			
14.1	Demographics Data		
14.1.1	Disposition		
14.1.1.1	Subject Disposition, Analysis Populations - All Subjects	IP	-
14.1.2	Demographics		
14.1.2.1	Subject Demographics – Safety Population	IP	-
14.1.2.2	Subject Demographics – PK Population	IP	14.1.2.1
14.1.2.3	Subject Demographics – Randomized Population	IP	14.1.2.1
14.2	Efficacy Data		
	Not Applicable	-	-
14.3	Safety Data		
14.3.1	Displays of Adverse Events		
14.3.1.1	Adverse Events, Overall Summary of TEAEs - Safety Population	IP	-
14.3.1.2	Adverse Events, Treatment Emergent Adverse Events by SOC and PT - Safety Population	IP	-
14.3.1.3	Adverse Events, Related Treatment Emergent Adverse Events by SOC and PT - Safety Population	IP	14.3.1.2

QMD Ref: Worldwide-TMP-ST-006-4.0 Effective: 12Aug2019	Governing QMD: Worldwide-SOP-ST-001
Confidentiality Statement	

This document is the property of Worldwide Clinical Trials Inc. and may not be duplicated, copied, altered or removed from company without prior approval from Worldwide Quality Assurance or in compliance with Worldwide Standard Operating Procedures.

Worldwide Clinical Trials Controlled Quality Management Document			
 WORLDWIDE CLINICAL TRIALS	Sponsor:	Cassava Sciences, Inc	
	Protocol Number:	PTI-125-05	
STATISTICAL ANALYSIS PLAN – PHASE 1			

Table Number	Table Title	Validation Method	Shell Number (if repeat)
14.3.1.4	Adverse Events, Serious Treatment Emergent Adverse Events by SOC and PT - Safety Population	IP	14.3.1.2
14.3.1.5	Adverse Events, Treatment Emergent Adverse Events leading to Early Withdrawal by SOC and PT - Safety Population	IP	14.3.1.2
14.3.1.6	Adverse Events, Treatment Emergent Adverse Events by SOC, PT and Maximum Severity - Safety Population	IP	-

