14.3.1.7	Adverse Events, Treatment Emergent Adverse Events by SOC, PT and Closest Relationship - Safety Population	IP	-
14.3.2	Listings of Deaths, Other Serious and Significant Adverse Events		
14.3.2.1	Adverse Event Leading to Death – Safety Population	IP	16.2.7.1
14.3.2.2	Serious Adverse Event Data – Safety Population	IP	16.2.7.1
14.3.3	Narratives of Deaths, Other Serious and Certain Other Significant Adverse Events		
14.3.4	Abnormal Laboratory Values		
14.3.4.1	Hematology Data, Descriptive Statistics - Safety Population	IP	-
14.3.4.2	Clinical Chemistry Data, Descriptive Statistics - Safety Population	IP	14.3.4.1
14.3.4.3	Urinalysis Data, Descriptive Statistics - Safety Population	IP	-
14.3.4.4	Hematology Data, Shift Summary - Safety Population	IP	-
14.3.4.5	Clinical Chemistry Data, Shift Summary - Safety Population	IP	14.3.4.4
14.3.4.6	Urinalysis Data, Shift Summary - Safety Population	IP	14.3.4.4
14.3.4.7	Out of Range Laboratory Data – Safety Population	IP	16.2.8.1
14.3.5	Vital Signs		
14.3.5.1	Vital Signs Data, Descriptive Statistics - Safety Population	IP	-
14.3.6	Other Safety		
14.3.6.1	12 Lead ECG, Descriptive Statistics - Safety Population	IP	-

QMD Ref: Worldwide-TMP-ST-006-4.0 Effective: 12Aug2019	Governing QMD: Worldwide-SOP-ST-001
Confidentiality Statement	

This document is the property of Worldwide Clinical Trials Inc. and may not be duplicated, copied, altered or removed from company without prior approval from Worldwide Quality Assurance or in compliance with Worldwide Standard Operating Procedures.

Worldwide Clinical Trials Controlled Quality Management Document			
 WORLDWIDE CLINICAL TRIALS	Sponsor:	Cassava Sciences, Inc	
	Protocol Number:	PTI-125-05	
STATISTICAL ANALYSIS PLAN – PHASE 1			

Table Number	Table Title	Validation Method	Shell Number (if repeat)
14.3.6.2	12 Lead ECG, Shift Summary - Safety Population	IP	-
14.4	PK Tables		
14.4.1	Descriptive Statistics of Simufilam Plasma Concentration-Time Data after Administration of Phase 3 Simufilam 100 mg Tablet under Fasted Conditions, with a Low-fat Breakfast, with a High-fat Breakfast, and after Administration of Phase 2 Simufilam 100 mg Tablet under Fasted Conditions– PK Population	IP	-

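### The maximum-severity and closest-relationship AE tables (14.3.1.6 and 14.3.1.7) count some subjects in several categories at SOC and Any TEAE level, so those rows do not show what the titles say

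*SAP*

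**What the plan says.** SAP 6.11.1 defines the severity table in two steps. At PT level, a subject with repeats of one PT in a treatment period is reduced to a single record: "it is counted once with maximum severity under the PT". At the next level the rule changes. The condition is "if a subject had multiple PTs within the SOC with different grades of maximum severity", and the consequence is that "it is counted once within each applicable severity grade within the SOC and Any TEAE categories".

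The relationship table has the same structure. Repeats of one PT collapse to the closest relationship, but across PTs in a SOC the subject is spread over the categories: "it is counted once within each applicable relationship category within the SOC and Any TEAE categories".

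SAP 6.2.5 sets the flags for maximum severity and closest relationship at the SOC-and-PT level within a treatment period. Neither section defines a single highest category per subject for a SOC or for all TEAEs.

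SAP 9 gives the titles. Table 14.3.1.6 is "Adverse Events, Treatment Emergent Adverse Events by SOC, PT and Maximum Severity - Safety Population" and Table 14.3.1.7 is "Adverse Events, Treatment Emergent Adverse Events by SOC, PT and Closest Relationship - Safety Population". The only footnote that the SAP text promises for its outputs concerns treatment sequences: "Footnotes will be added in all TLFs to clarify each sequence".

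**The concern.** A reader of a table by maximum severity will take the mild row under a SOC, or under Any TEAE, as the subjects whose worst event was mild. The same reader will expect mild, moderate and severe to be mutually exclusive and to add up to the subjects with a TEAE. Under the stated rule neither holds for a subject with two or more PTs in one SOC at different maxima. That subject also appears in a lower category that is not their maximum at that level. In the relationship table, likewise, a subject with a probably related event can also appear as unlikely or possible.

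What is at stake is the correct reading of the lower-category rows in two descriptive safety tables. The PT rows in the treatment columns, the count in each subject's highest category, and Table 14.3.1.2 are not affected.

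**Working it through.** The documents give no figure for this point, so the check is to apply the counting rule to data.

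**Inputs**
- PT-level and SOC-level counting rules: SAP 6.11.1.
- Three severity grades (Protocol 8.2) and three relationship categories (Protocol 8.3).
- 24 planned subjects: Protocol 9.5 and SAP 4.
- Percentage base: SAP 6.3 says "Percentages will be based on the number of non-missing observations or the subject population unless otherwise specified". I assume the subject population, with all 24 dosed in the treatment shown.

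**Hypothetical data: one treatment column, one SOC, PTs P and Q**
- Subject 1: P mild, then P moderate.
- Subject 2: P mild and Q moderate.
- Subject 3: P mild.

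**Step 1, maximum per subject and PT.** Subject 1: P moderate. Subject 2: P mild, Q moderate. Subject 3: P mild. The PT rows are therefore P mild 2, P moderate 1, Q moderate 1, whichever rule is used higher up.

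**Step 2, SOC row and Any TEAE row** (identical here, because there is one SOC)

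| Grade | SAP rule | One count at worst grade |
|---|---|---|
| Mild | subjects 2, 3: 2/24 = 8.3% | subject 3: 1/24 = 4.2% |
| Moderate | subjects 1, 2: 2/24 = 8.3% | subjects 1, 2: 2/24 = 8.3% |
| Severe | 0 | 0 |
| Sum | 4/24 = 16.7% | 3/24 = 12.5% |

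Three subjects had a TEAE, and only the right-hand column adds to three. Subject 2 makes the whole difference. Subject 1, with repeats of a single PT, is handled correctly by the SAP rule.

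**Upper limit per subject.** Extra entries in a SOC or Any TEAE block = number of distinct PT-level maxima − 1. With three categories this is at most 3 − 1 = 2.

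**Single-subject checks** (mild/moderate/severe in the SOC and Any TEAE rows)
- One PT mild and another severe: SAP rule 1/0/1, worst grade 0/0/1.
- Three PTs, one at each grade: SAP rule 1/1/1, worst grade 0/0/1.
- One PT twice, mild then severe: 0/0/1 under both.

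The relationship table behaves in the same way with unlikely, possible and probable in place of the grades.

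**Two cases the text leaves open.** The condition covers PTs within one SOC, so counting in Any TEAE for PTs in different SOCs is not stated. The PT collapse works within a treatment period, although AEs are also summarized in a total column, so counting across periods in that column is not stated.

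**The case against.** The strongest reply is that the rule is explicit and prespecified, can be programmed without ambiguity, and agrees with SAP 6.2.5, which flags the maximum at PT level. On that reading the titles refer to a PT-level maximum and only labelling is in dispute. The mock shells, which were not available for this review, may carry a footnote on the overlap. Subject counts by SOC and PT appear in Table 14.3.1.2, and all AEs are listed. The situation also needs one subject with two PTs in the same SOC at different maxima in one period of a single-dose study. Protocol 2.3 reports no drug-related AEs in the single ascending dose study at 50 to 200 mg.

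Much of this stands. The rule is clear, few subjects are likely to be affected, and no signal is lost. But SAP 6.2.5 only confirms that the maximum stops at PT level; it does not make a SOC or Any TEAE row a maximum. A footnote in the shells could explain the overlap but would not change the counts. Table 14.3.1.2 gives subjects with an event, not subjects by worst grade. SAP 6.11.1 does not say how the overall summary, Table 14.3.1.1, counts subjects by severity, so it cannot be relied on for that count either.

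**Conclusion.** The concern holds: the rule is wrong as written for tables with these titles. Followed exactly, the lower-category SOC and Any TEAE rows of Tables 14.3.1.6 and 14.3.1.7 can include subjects whose worst or closest-related event was in a higher category.

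The size is minor. The number of subjects affected cannot be known in advance and is probably small among 24 volunteers given single doses. The example shows how the rule works and is not an estimate of frequency; its percentages assume all 24 are dosed. Neither the count of severe or probably related events nor the PK objectives are affected. Confidence is high on what the rule does. Whether a reader would be misled depends partly on the unseen shells.

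**What to change.** Replace both SOC-level clauses in SAP 6.11.1 with a rule of this kind: within each SOC, and within Any TEAE across all SOCs, a subject is counted once per treatment at the highest severity (or closest relationship) across their PTs; in the Total column, once across all treatments. This makes the categories mutually exclusive and settles the two open cases, PTs in different SOCs and the Total column. Add matching SOC-level and subject-level flags to SAP 6.2.5.

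If multiple counting is intended, keep the rule, retitle both tables, and footnote that the SOC and Any TEAE categories overlap and do not add up to the number of subjects.

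The first option costs two sentences in 6.11.1, a matching line in 6.2.5 and a small programming change. The second costs two titles and a footnote. Neither needs any new data.

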## 6.11.2 Laboratory Data

### 6.11.2.1 Descriptive Summaries

Hematology, Serum Chemistry and Urinalysis assessment at Baseline and EOS/ET will be summarized. Descriptive statistics of the observed values and change from baseline will be presented by visit for each Hematology, Serum Chemistry and Urinalysis listed below for Safety Population. Only total column will be presented. For Urinalysis, categorical results will be presented in the same table and percentages will be based on number of subjects with non-missing assessments within each visit.

All laboratory parameters will be listed in the order given below and in units in compliance with CDISC Controlled Terminology version 2020-11-06 or later.

**Hematology:** White blood cell (WBC) count with differential, red blood cell (RBC) count, hemoglobin, hematocrit, platelet count

**Serum Chemistry:** glucose, sodium, potassium, chloride, bicarbonate, blood urea nitrogen (BUN), creatinine, uric acid, phosphorus, calcium, total protein, albumin, globulin, alkaline phosphatase, alanine transaminase (ALT), aspartate transaminase (AST), total bilirubin, lactate dehydrogenase (LDH)

**Urinalysis:** color, specific gravity, pH, protein, sugar, ketones, occult blood

In Mock Shells: Tables 14.3.4.1 and 14.3.4.3

QMD Ref: Worldwide-TMP-ST-006-4.0 Effective: 12Aug2019	Governing QMD: Worldwide-SOP-ST-001
Confidentiality Statement	

This document is the property of Worldwide Clinical Trials Inc. and may not be duplicated, copied, altered or removed from company without prior approval from Worldwide Quality Assurance or in compliance with Worldwide Standard Operating Procedures.

Worldwide Clinical Trials Controlled Quality Management Document			
 WORLDWIDE CLINICAL TRIALS	Sponsor:	Cassava Sciences, Inc	
	Protocol Number:	PTI-125-05	
STATISTICAL ANALYSIS PLAN – PHASE 1			

### 6.11.2.2 Shift Summary

Shift summaries of the Normal range indicator (Low/Normal/High) will be presented at EOS/ET visit for Safety Population.

All laboratory data including Pregnancy tests, FSH tests, Urine Drug, Alcohol, and Cotinine Screens and Serology will be listed. Out of normal range laboratory results will be separately listed.

In Mock Shells: Tables 14.3.4.4 and 14.3.4.6, 14.3.4.7, Listing 16.2.8.1 to 16.2.8.6

### 6.11.3 Vital Signs

Vital signs will be measured once in Screening and Day 8 (discharge); on Day 1, Day 3, Day 5, and Day 7 at following timepoints: predose (1 hour), postdose 30 and 90 min, and 4, 8, 12 hours post-dose (within 15 min of nominal time); on Day 2, Day 4 and Day 6 at timepoints 4 h and 12 h, and at any other time deemed medically necessary. Vital signs will be measured after a 3-minute sitting period.

Vital Signs results at Baseline and all post-baseline timepoints will be summarized. Descriptive statistics for observed values and changes from Baseline in the following vital signs parameters will be presented by treatment at each visit/timepoint for Safety Population. Screening, results will only be listed. All parameters will be listed in the order given below and in units collected.

- Systolic blood pressure (mmHg)
- Diastolic blood pressure (mmHg)
- Heart rate (beats/min)
- Respiration rate (breath/min)
- Temperature (°C)

All vital signs data will be listed.

In Mock Shells: Tables 14.3.5.1, Listing 16.2.8.7

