**Table 1 Treatment Sequences by Period**

Sequence	Treatment Period -1				Treatment Period -2				Treatment Period -3				Treatment Period -4			
	Fasted	High	Low	Phase 2 Tablet	Fasted	High	Low	Phase 2 Tablet	Fasted	High	Low	Phase 2 Tablet	Fasted	High	Low	Phase 2 Tablet
Sequence A (n = 6)				X			X		X					X		
Sequence B (n = 6)	X							X		X					X	
Sequence C (n = 6)		X			X						X					X
Sequence D (n = 6)			X			X						X	X			

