### 6.2.1 Treatment Period / Visits

Each visit as per study schedule will be mapped to treatment period and analysis visit for summary tables as given below. Listings will reflect actual period and visit as defined in protocol.

Collected visit	Treatment Period	Analysis visit
Screening	-	Screening
DAY 0 Check-in	-	Check-in
DAY 1	Period 1	Day 1
DAY 2	Period 1	Day 2
DAY 3	Period 2	Day 3
DAY 4	Period 2	Day 4
DAY 5	Period 3	Day 5
DAY 6	Period 3	Day 6
DAY 7	Period 4	Day 7
DAY 8	Period 4	EOS / ET
Early Termination	Subject's last treatment period	EOS / ET

QMD Ref: Worldwide-TMP-ST-006-4.0 Effective: 12Aug2019	Governing QMD: Worldwide-SOP-ST-001
Confidentiality Statement	

This document is the property of Worldwide Clinical Trials Inc. and may not be duplicated, copied, altered or removed from company without prior approval from Worldwide Quality Assurance or in compliance with Worldwide Standard Operating Procedures.

Worldwide Clinical Trials Controlled Quality Management Document			
 WORLDWIDE CLINICAL TRIALS	Sponsor:	Cassava Sciences, Inc	
	Protocol Number:	PTI-125-05	
STATISTICAL ANALYSIS PLAN – PHASE 1			

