## 6.2.3 Baseline

Baseline is defined as the last non-missing value (either scheduled, unscheduled or repeat) before the subject receives the first dose of study drug.

For variables that will be summarized by treatment, the baseline for each period is defined as the last non-missing value (either scheduled, unscheduled or repeat) that is collected before dosing of respective period.

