### 6.2.10 PK Parameters

Concentration-time data for simufilam will be analyzed using noncompartmental methods in Phoenix™ WinNonlin® (Version 8.1 or higher, Certara, L.P.) in conjunction with the internet-accessible implementation of Pharsight® Knowledgebase Server™ (PKSO; Version 4.0.4, Certara, L.P.). Concentrations that are below the limit of quantification (BLQ) will be treated as zero in the data summarization and descriptive statistics.

QMD Ref: Worldwide-TMP-ST-006-4.0 Effective: 12Aug2019	Governing QMD: Worldwide-SOP-ST-001
Confidentiality Statement	

This document is the property of Worldwide Clinical Trials Inc. and may not be duplicated, copied, altered or removed from company without prior approval from Worldwide Quality Assurance or in compliance with Worldwide Standard Operating Procedures.

Worldwide Clinical Trials Controlled Quality Management Document			
 WORLDWIDE CLINICAL TRIALS	Sponsor:	Cassava Sciences, Inc	
	Protocol Number:	PTI-125-05	
STATISTICAL ANALYSIS PLAN – PHASE 1			

Blood samples for PK samples for the determination of simufilam will be collected at pre-dose (0), and at 0.333 (20 min), 0.667 (40 min), 1, 1.5, 2, 2.5, 3, 4, 6, 8, 10, 12, and 24 hours post-dose, for each treatment period.

Mean plasma concentration-time data will be presented graphically on both linear and semi-log scales using nominal time. Spaghetti plots and individual plots will be presented on both linear and semi-log scales using actual time. The following plots will be created:

- 1) Mean plot: Phase 3 Simufilam Tablet Fasted, Low-fat, and High-fat
- 2) Mean plot: Phase 2 Simufilam Tablet Fasted, Phase 3 Simufilam Fasted
- 3) All Subject plot: All subjects in one plot per Treatment
- 4) Individual Subject plot: Phase 3 Simufilam Tablet Fasted, Low-fat, and High-fat plotted together for each subject
- 5) Individual Subject plot: Phase 2 Simufilam Tablet Fasted, Phase 3 Simufilam Fasted plotted together for each subject

Individual plasma concentrations from subjects that were excluded from the PK Analysis Population will be listed in Concentration Listings.

Concentration-time data for simufilam in plasma will be analyzed using non-compartmental methods. The following descriptive statistics will be presented by treatment and nominal time: sample size (N), arithmetic mean, standard deviation (SD), coefficient of variation (CV%), minimum, median, and maximum.

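### Does the SAP need a rule that pools vital signs across the four crossover periods?

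*SAP*

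**What the plan says.** Under SAP 6.11.3, observed vital signs and their changes from baseline "will be presented by treatment at each visit/timepoint for Safety Population". The collection times are pre-dose, 30 and 90 min, and 4, 8 and 12 h on Days 1, 3, 5 and 7; 4 h and 12 h on Days 2, 4 and 6; and once on Day 8. The layout is referred to mock shell Table 14.3.5.1, which is not part of the public documents.

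SAP 6.2.1 says that visits "will be mapped to treatment period and analysis visit for summary tables as given below". Its table keeps Days 1 to 7 separate. The only merge is Day 8 with early termination, as EOS/ET.

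Three other sections bear on the layout:

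- SAP 6.2.3: "For variables that will be summarized by treatment, the baseline for each period is defined as the last non-missing value" before that period's dose.
- SAP 6.3: "Summaries of the clinical data will be presented by treatment group / sequence or overall".
- SAP 6.11: "The safety analyses will be presented by the treatment received for the Safety Analysis Set".

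Elsewhere the SAP is more explicit about rows and columns. For PK concentrations (SAP 6.2.10), "The following descriptive statistics will be presented by treatment and nominal time". For laboratory data (SAP 6.11.2.1), "Only total column will be presented", and SAP 6.11.4.1 has the same rule for ECG. Protocol 9.4 asks for a descriptive summary of vital signs as change from screening and is silent on periods.

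**The concern.** In a crossover, the natural safety display puts the same subjects under every treatment at the same time since dose. Here the summary visit is defined as a study day, and on each dosing day the four treatments go to four different sequences. A programmer who follows the text literally would produce a long table of six-subject cells in which no row compares treatments in the same people. A difference between columns in one row would then mix the treatment with who happened to be in that sequence.

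Pooling by time since dose would put all 24 subjects in each treatment column of the dosing-day rows. Each treatment is given once in every period, so any drift over the week of confinement would be balanced across columns. What is at stake is how easily one safety table can be read.

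**Working it through.** **Inputs.** Four sequences of 6 subjects (SAP 5), so 4 × 6 = 24, which reproduces the stated enrolment. Treatment order is from SAP 5 ("Table 1 Treatment Sequences by Period"). Measurement times are from SAP 6.11.3 and the visit mapping is from SAP 6.2.1. Full enrolment, no dropout and dosing as planned are assumed.

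**Who is in each cell**

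| Treatment | Day 1 | Day 3 | Day 5 | Day 7 |
|---|---|---|---|---|
| Fasted | B | C | A | D |
| High-fat | C | D | B | A |
| Low-fat | D | A | C | B |
| Phase 2 tablet | A | B | D | C |

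All 16 cells hold exactly one sequence, n = 6. Days 2, 4 and 6 follow the dosing day before them, and Day 8 follows Day 7.

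**Cells per parameter, literal reading** (blood pressure, heart rate, respiration rate)

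- Dosing days: 4 treatments × 4 days × 6 times = 96
- Washout days: 4 × 3 × 2 = 24
- Day 8: 4
- Total: 96 + 24 + 4 = 124, all n = 6

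**Cells per parameter, pooled by time since dose**

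- Dosing-day times: 4 × 6 = 24, each n = 24
- Washout-day times: 4 × 2 = 8, each n = 18, because Period 4 has no washout-day 4 h and 12 h measurements
- Day 8: 4, each n = 6, since pooling cannot alter a single end-of-study measurement
- Total: 24 + 8 + 4 = 36

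Protocol 6.5.3 to 6.5.6 take temperature pre-dose, on washout days and on Day 8 only. Its counts are 16 + 24 + 4 = 44 literal and 4 + 8 + 4 = 16 pooled. Showing Day 8 in one total column would lower the pooled counts to 33 and 13, but that is a separate display choice.

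**Overlap between columns in one row.** Literal: 0 subjects. Pooled dosing-day rows: 24 of 24. Pooled washout rows: each treatment lacks a different sequence (Fasted D, High-fat A, Low-fat B, Phase 2 tablet C), so any two columns share 2 sequences, or 12 of 18 subjects.

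**Can the pooled table be recovered from the literal one?** For cells i with n_i subjects, mean m_i and SD s_i, and N = Σn_i:

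- pooled mean m = Σn_i m_i / N
- pooled variance = [Σ(n_i − 1)s_i² + Σn_i(m_i − m)²] / (N − 1)

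With four cells of 6 this is [5Σs_i² + 6Σ(m_i − m)²] / 23. The pooled minimum and maximum are the extremes over the cells. Only the median cannot be rebuilt from the cells, and it can be computed from Listing 16.2.8.7.

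**Precision.** A 95% interval for a mean has half-width t × SD/√n: 1.05 SD at n = 6 and 0.42 SD at n = 24. SAP 6.11.3 plans no intervals or tests for vital signs, so this difference enters no planned output.

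**The case for a change.** The strongest argument for a change is that the plan never states the rule. SAP 6.2.1 was the place to combine dosing days and did not do so. A period-specific baseline works equally well in a day-by-day table, and presentation by treatment received fixes the columns but not the rows. That is right: the cited sections fit pooling without stating it. The PK wording does not use the word pooled either. It is read that way because it names no visit, and the vital-signs wording, which joins visit and timepoint, is open to either reading.

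A second argument is that the washout-day values carry the same 4 h and 12 h labels as the dosing-day values. Protocol 6.5.4 counts them from that morning's PK sample, so they fall near 28 h and 36 h after dosing if that is the 24 h sample. Pooling on the label alone would mix different times. This deserves care in programming, but the values belong to separate analysis visits (Days 2, 4 and 6), which keeps them apart unless someone discards the visit.

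The loss under the literal reading is also narrower than it seems. Sequence B appears under Fasted on Day 1, the Phase 2 tablet on Day 3, High-fat on Day 5 and Low-fat on Day 7. The same six people are therefore in all four columns at the same times since dose, in different rows. What is missing is a comparison within one row.

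The reference value for change (screening in protocol 9.4, pre-dose baseline in the SAP, with SAP 7 declaring no changes) is a different question, which a pooling rule neither creates nor settles.

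**Conclusion.** No change to the plan is called for. The SAP leaves a display rule unwritten, and an analyst with the shell and the period-specific baseline can fill it sensibly. If the table were produced by day, it would be sparse but correct: 124 cells of n = 6 per parameter instead of 36, and 44 instead of 16 for temperature. It would still hold the information needed to rebuild every pooled statistic except the median, which the listing supplies. No test, estimate or conclusion rests on the layout, and the PK analysis is untouched.

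The counts assume 24 subjects, no dropout or replacement, and dosing as planned. With an early termination, an EOS/ET cell could mix sequences, because SAP 6.2.1 assigns that visit to the subject's last period. The shell for Table 14.3.5.1 could not be seen and may already settle the layout.
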